11.4.4.8. Other Safety Analysis

Not applicable.

11.4.5. Other Analysis

Not applicable.

11.4.6. Interim and Independent Data Monitoring Committee Analyses

11.4.6.1. Interim Analysis

Not applicable.

11.4.6.2. Independent Data Monitoring Committee Analysis

Not applicable.

12. PROCEDURAL, ETHICAL, REGULATORY, AND ADMINISTRATIVE CONSIDERATIONS

12.1. Adverse Event

12.1.1. Definition

An **adverse event (AE)** is defined as any untoward medical occurrence in a subject participating in a clinical investigation. This AE does not necessarily need to have a causal relationship with the treatment. An AE can therefore be any unfavorable and unintended sign (e.g., a clinically significant abnormal laboratory finding), symptom, or disease temporally associated with the use of an investigational product, whether or not related to the investigational product.

A **suspected adverse reaction (SAR)** is any AE for which there is a reasonable possibility that the study treatment caused the adverse event. ‘Reasonable possibility’ means that there is evidence to suggest a causal relationship between the study treatment and the AE. A suspected adverse reaction implies a lesser degree of certainty about causality than adverse reaction, which means any AE caused by a study treatment.

An AE may be:

- A new illness,
- Worsening of a concomitant illness or a baseline event,
- An effect of the study treatment; it could be an abnormal laboratory value as well as a significant shift from baseline within normal range which the Principal Investigator or medically qualified designate considers to be clinically important.

Surgical procedures themselves are not AEs. They are therapeutic measures for conditions that required surgery. The condition for which the surgery is required is an AE, if it occurs or is detected during the treatment period. Planned surgical measures permitted by the clinical study protocol and the condition(s) leading to these measures are not AEs, if the condition(s) was (were) known before the start of study treatment. In the latter case, the condition should be reported as medical history.

A **serious adverse event (SAE)** or reaction is any untoward medical occurrence that at any dose:

- Results in death,
- Is life-threatening,
- Requires nonscheduled (not routine or planned) subject hospitalization for ≥ 24 hours or prolongation of existing hospitalization for ≥ 24 hours,
- Results in persistent or significant disability or incapacity (defined as a substantial disruption of a person’s ability to conduct normal life functions),
- Is a congenital anomaly or birth defect,

- Is an important medical event defined as an event that does not fit one of the other outcomes but may jeopardize the subject and may require medical or surgical intervention (treatment) to prevent one of the other outcomes. Examples include allergic bronchospasm (a serious problem with breathing) requiring treatment in an emergency room, serious blood dyscrasias (blood disorders), or seizure/convulsion that does not result in hospitalization. The development of drug dependence or drug abuse would be other examples of important medical events.
- All AEs that do not meet any of the criteria for seriousness should be regarded as ***non-serious AEs***
- **A pre-existing condition** is one that is present at the start of the study. A pre-existing condition should be recorded as an AE if the frequency, intensity, or the character of the condition worsens during the study period.
- At the end of the study, any new clinically significant findings/abnormalities that meet the definition of an AE must also be recorded and documented as an AE.

12.1.1.1. Severity Assessment

The investigator or the designated person will provide an assessment of the severity of each AE by recording a severity rating on the appropriate AE reporting page of the subject's CRF. In classification of AEs, the term "severe" is not the same as "serious". Severity is a description of the intensity of a specific event. The term "serious" relates to a subject/event outcome or action criteria, usually associated with events that pose a threat to a subject's life or functioning.

All adverse events will be graded according to the severity scale below. General descriptions of each severity grade may be found in [Table 11](#).

Table 11: General Descriptions of Severity Scale

Severity Scale	General Descriptions
Mild	Asymptomatic or mild symptoms; clinical or diagnostic observations only; intervention not indicated; The AE is easily tolerated and does not interfere with daily activities.
Moderate	Minimal, local or noninvasive intervention indicated; The AE interferes with daily activities, but the subject is still able to function.
Severe	Not immediately life-threatening; hospitalization or prolongation of hospitalization indicated; disabling; The AE is incapacitating and requires medical intervention.

Every effort will be made to obtain an adequate evaluation of the severity.

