11.4.4.1. Adverse Events

Adverse events will be coded according to Medical Dictionary for Regulatory Activities (MedDRA). The number and percentage of subjects experiencing an adverse event will be summarized by the MedDRA system organ class and preferred term, as well as by dose received. Adverse events will be classified as pre-treatment or treatment-emergent.

Pre-treatment adverse events are defined as adverse events that were reported or worsened after signing the ICF up to start of study medication.

Treatment-emergent adverse events are defined as adverse events that were reported or worsened on or after start of study medication through the Follow-up visit.

Only treatment-emergent adverse events will be summarized in tables. Treatment-emergent adverse events will hereafter be referred to as “adverse events.”

The incidence of adverse events will be summarized. Adverse event summaries will include the following:

- All adverse events (regardless of severity or relationship to study drug)
- SAEs
- Adverse events by severity
- Adverse events by relationship to study drug
- Adverse events leading to discontinuations
- Adverse events leading to deaths

Adverse event summaries will be presented by MedDRA System Organ Class and Preferred Term. A subject with multiple occurrences of the same adverse event or a continuing adverse event will be counted once, and only the maximum severity level will be presented in the severity summaries, and the worst relationship level in the relationship summaries.

Adverse events will be listed separately for those leading to death, SAEs, dose interruption, and permanent discontinuation.

All adverse events through the Follow-up visit will be listed in an individual subject data listing, including pre-treatment adverse events.

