12.1.3. Serious Adverse Reporting

The investigator or any other study center personnel's knowledge will notify any SAEs including fatal or life-threatening to SK Life Science, Inc. (SKLSI) and their designee **IQVIA** on an **SAE report form**, without regard to causality, within 24 hours after becoming aware of its occurrence.

If, during follow-up, any non-serious AE worsens and eventually meets the criteria for an SAE, that AE should be recorded as a new SAE.

The initial SAE report must be as complete as possible, including details of the current illness and SAE, and an assessment of the causal relationship between the event and the investigational product. Information not available at the time of the initial report (e.g., an end date for the AE, laboratory values received after the report, or hospital discharge summary) must be documented and an updated SAE report form should be forwarded to the Sponsor and their designee **IQVIA** within 24 hours of new/updated information. All follow-up information must be reported as soon as the relevant information is available. The notification of all SAE's should be directed to the following Sponsor representatives ([Table 13](#) and [Table 14](#)).

Table 13: Contact Information for IQVIA

Name	IQVIA
Email	[contact]
[contact]
[contact]

Table 14: Contact Information for Sponsor Medical Monitor

Name	[name]
Email	[contact]
[contact]
[contact]

At the time of the initial SAE report, the investigator should provide as much of the following information as possible:

- Study identifier
- Study site
- Subject number
- A description of the event
- Date of onset
- Current Status
- Whether study drug was discontinued
- The reason why the event is classified as serious
- Investigator's assessment of the association between the event and study drug

The Sponsor will be responsible for evaluating the events for expedited reporting, and for reporting them to the applicable regulatory agencies.

If reports of any new and unexpected AEs become available to the Sponsor during the clinical portion of this study (related or not to the present study), the Sponsor has to advise the clinical site, through its Principal Investigator, of those events.

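### The mandatory AE severity scale (Protocol, Table 11) has no grade whose description admits an immediately life-threatening or fatal event

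*Protocol*

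**What the plan says.** Section 12.1.1.1 makes grading compulsory and universal. The investigator or designated person "will provide an assessment of the severity of each AE by recording a severity rating", and "All adverse events will be graded according to the severity scale below". Table 11 then gives three grades. Mild is for events that are easily tolerated. Moderate is for events that interfere with daily activities but leave the subject able to function. Severe, the highest, reads: "Not immediately life-threatening; hospitalization or prolongation of hospitalization indicated; disabling; The AE is incapacitating and requires medical intervention". The same section keeps severity (intensity) apart from seriousness (outcome or action criteria).

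The grade is used in Section 11.4.4.1, which plans summaries by severity: "A subject with multiple occurrences of the same adverse event or a continuing adverse event will be counted once, and only the maximum severity level" is shown. Adverse events are part of the primary safety endpoint (Section 6.1).

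Other sections foresee the gravest events. Section 12.1.1 lists death and "Is life-threatening" among the SAE criteria. Section 11.4.4.1 plans a summary headed "Adverse events leading to deaths". Section 8.4 covers a life-threatening reaction that puts the subject at immediate risk. Section 7.3 names severe and life-threatening events side by side.

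**The concern.** A severity scale applied to all events should be exhaustive: every event that can occur should fit one grade. Here the highest grade begins by excluding the most intense events, and nothing stands above it. For an immediately life-threatening or fatal event, the instruction to grade on Table 11 cannot be followed as written.

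What is at stake is the meaning of the top row of the severity table. Only the maximum grade per subject is shown, so the top of the scale carries the most weight in that summary. If a life-threatening or fatal event is entered as Severe, a reader who takes Severe at its printed meaning will misread the row.

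**Working it through.** No sample-size or rate calculation is involved, and the protocol states no figure to reproduce. The check sets the grade descriptions against the events that the protocol foresees.

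**Step 1: is grading optional for any event?** No. Section 12.1.1.1 requires a rating for each event and applies the scale to all of them.

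**Step 2: does an immediately life-threatening or fatal event fit a grade?**

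| Grade | Decisive part of the description | Admits such an event? |
|---|---|---|
| Mild | easily tolerated | No |
| Moderate | subject still able to function | No |
| Severe | opens by excluding immediate threat to life | No |

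Count: 0 of 3 grades.

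**Step 3: does another section assign such an event to a grade?** None does. Section 12.1.1 makes it serious, but Section 12.1.1.1 says that severe and serious are different things, so the SAE flag does not supply a severity grade.

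**Step 4: does the protocol expect that such events could occur?** Yes, in Sections 7.3, 8.4, 11.4.4.1 and 12.1.1. Section 12.1.3 also asks sites to report them: the site "will notify any SAEs including fatal or life-threatening to SK Life Science, Inc". Sections 7.3 and 12.1.1 speak of life-threatening events without the word immediately. The clearest cases outside the printed scale are therefore the immediate-risk reaction in Section 8.4 and fatal events.

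**Step 5: what would be recorded?** A rating must be entered, and Mild and Moderate are plainly wrong. Severe is the only plausible choice, and the rest of its description (incapacitating, needing medical intervention) is met. The probable entry is therefore Severe, contrary to that grade's opening phrase.

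**Step 6: where does the entry go?** It goes into the severity summary of Section 11.4.4.1, in the same row as events that fit the Severe description. The SAE and death summaries in that section do not depend on the grade.

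**The case against.** The strongest reply is that this is a loose label. Table 11 is offered as general descriptions, raters will use Severe, and threat to life is captured on the seriousness axis. Section 10.6.1 adds that Section 12.1 is only a brief outline, and that detailed eCRF completion guidelines and training on adverse events will be provided. Much of this stands. It explains why the practical effect is small, and the guidelines may well tell raters what to do. But a general description can excuse an imperfect fit more easily than an express exclusion. Table 11 is the only scale the protocol gives, and guidelines that are not at hand cannot be shown to cure it. An SAP could not fully repair it either, because the investigator or designee records the grade on the CRF under the protocol's scale.

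It is also fair that deleting the excluding phrase alone would leave the expected table unchanged: the event would be Severe before and after. Only an added level separates it.

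Four stronger readings are tempting and are not supported:

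- **Different raters would grade such events differently.** Severe is the only plausible choice, so the text shows no competing grade.
- **Subjects would drop out of the severity table.** The rating is compulsory, so no blank field is foreseen.
- **The cohort stopping criterion is undermined.** Section 7.3 names life-threatening events expressly and does not rely on Table 11 having a grade for them.
- **The size of the problem is one subject as a share of a small active cohort.** That share only restates cohort size. It says nothing about the defect and would be the same after the excluding phrase was deleted.

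**Conclusion.** The error is real and minor. As printed, 0 of 3 grades admits an immediately life-threatening or fatal event, so a compulsory grading rule cannot be followed for the gravest events the protocol foresees. The consequence is limited to one CRF field and one family of summaries, where such an event would probably sit under Severe beside events that fit the description.

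This rests on two assumptions: that the opening phrase of the Severe description is read as it is written, and that raters will choose Severe when nothing fits. The effect arises only if such an event occurs, and the protocol gives no expected rate. It is an internal-consistency error in the grading scale. The choice of analysis is not at fault.

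**What to change.** Preferred: add one level above Severe to Table 11 for life-threatening or fatal events. Use it in the CRF severity field and in the severity summaries of Section 11.4.4.1, and align the eCRF completion guidelines and training mentioned in Section 10.6.1. The maximum-severity rule and Section 7.3 can stay as they are. The cost is one table row, one code value and matching guideline and training text, with no new assessment.

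At minimum: delete the opening phrase of the Severe description, so that the top grade is open-ended and the scale is exhaustive. This costs a few words in one cell. It removes the contradiction but does not separate these events from other Severe events in the severity table. The SAE and death summaries would continue to identify them.

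Either change is best made before events are graded, since a later change could mean regrading.

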12.1.1.2. Causality Assessment

An assessment should be made of the causal relationship of the adverse event to the study treatment, i.e., according to the following definitions in [Table 12](#).

Table 12: Definitions of Causality Assessment

Causality Assessment	Definitions
Unrelated	The event is occurring before dosing The event is definitely produced by the subject's clinical state or by other modes of therapy administered to subject
Remote	The event does not follow a reasonable (poor) temporal relationship with drug treatment And/or the event is readily explained by the subject's clinical state or by other modes of therapy administered to subject
Possible	Reasonable temporal relationship with drug treatment But the event could have been produced by the subject's clinical state or by other modes of therapy administered to subject
Probable	Reasonable temporal relationship with drug treatment, abates upon discontinuation of drug And/or event cannot be reasonably explained by the known characteristics of the subject's clinical state.
Definite	Distinct temporal relationship with drug treatment, abates upon discontinuation of drug (de-challenge) and is confirmed by reappearance of the reaction on repeat exposure (re-challenge)

Adverse events must be followed until resolution by the Principal Investigator. Resolution is defined as the return to baseline status or stabilization of the condition with the expectation that it will remain chronic. Adverse events that are not serious and are ongoing at the subject's last visit will be followed for a maximum of 30 days. Serious adverse events that are not resolved or stabilized during this time period will be followed until resolution or stabilization.

12.1.2. Routine Reporting

For the purposes of this study, the period of observation of adverse events for each subject extends from the signing of the informed consent form until their last visit including the follow-up visit or early termination, whichever is longer.

All events reported by the subject, observed by the clinical staff (events, such as abnormal, clinically significant findings from physical examinations, ECG tracings, laboratory assessments, and vital sign measurements), or elicited by general questioning will be recorded in the Institution's source document and reported as an adverse event and captured in the adverse events CRF. If necessary, every effort will be made to obtain an adequate

follow-up of the subjects. Should any subject choose to withdraw early from the study, they will be advised of the safety precautions to be taken.

Early Termination and End of Study (EOS) visit assessments should be performed, including the following: medical history, vital signs, physical exam, safety and clinical laboratory tests, ECG, peak expiratory flow rate (PEFR), Columbia-Suicide Severity Rating Scale (C-SSRS), and adverse event/concomitant monitoring.

Subjects will be questioned on their health status at the beginning of each visit and before their departure from the clinical site. Open-ended questions will be asked.

Classification will be performed by System Organ Class (SOC) and Preferred Term (PT) using the latest version of Medical Dictionary for Regulatory Activities (MedDRA) at the start of the study.

In general, AEs occurring secondary to other events (e.g., clinical sequelae or a cascade of events) should be identified by their primary cause. For example, if severe vomiting is known to result in dehydration, it is sufficient to record only vomiting as SAE or AE in the CRF. However, medically significant AEs occurring secondary to an initiating event that are separated in time should be recorded as independent events on the CRF.

12.1.3. Serious Adverse Reporting

The investigator or any other study center personnel's knowledge will notify any SAEs including fatal or life-threatening to SK Life Science, Inc. (SKLSI) and their designee **IQVIA** on an **SAE report form**, without regard to causality, within 24 hours after becoming aware of its occurrence.

If, during follow-up, any non-serious AE worsens and eventually meets the criteria for an SAE, that AE should be recorded as a new SAE.

The initial SAE report must be as complete as possible, including details of the current illness and SAE, and an assessment of the causal relationship between the event and the investigational product. Information not available at the time of the initial report (e.g., an end date for the AE, laboratory values received after the report, or hospital discharge summary) must be documented and an updated SAE report form should be forwarded to the Sponsor and their designee **IQVIA** within 24 hours of new/updated information. All follow-up information must be reported as soon as the relevant information is available. The notification of all SAE's should be directed to the following Sponsor representatives ([Table 13](#) and [Table 14](#)).

Table 13: Contact Information for IQVIA

Name	IQVIA
Email	[contact]
[contact]
[contact]

Table 14: Contact Information for Sponsor Medical Monitor

Name	[name]
Email	[contact]
[contact]
[contact]

At the time of the initial SAE report, the investigator should provide as much of the following information as possible:

- Study identifier
- Study site
- Subject number
- A description of the event
- Date of onset
- Current Status
- Whether study drug was discontinued
- The reason why the event is classified as serious
- Investigator's assessment of the association between the event and study drug

The Sponsor will be responsible for evaluating the events for expedited reporting, and for reporting them to the applicable regulatory agencies.

If reports of any new and unexpected AEs become available to the Sponsor during the clinical portion of this study (related or not to the present study), the Sponsor has to advise the clinical site, through its Principal Investigator, of those events.

12.1.4. Laboratory Results as Adverse Events

The determination of whether laboratory test results are clinically significant should be made by a physician or by a clinical study staff member (listed on Form FDA 1572) who is qualified to review and assess laboratory tests. This determination is important, as a clinically significant laboratory abnormality must be associated with an adverse event, either directly or indirectly as explained below.

The criteria for determining whether an abnormal laboratory test finding should be clinically significant are as follows:

Test result is associated with clinical signs or symptoms. If the signs or symptoms are related to a diagnosis that has already been documented as an adverse event, the lab abnormality itself generally does not have to be reported as an additional adverse event (e.g., hyperglycemia with an adverse event of new-onset diabetes; if diabetes is documented as an adverse event, hyperglycemia does not need to be documented separately as it is a common finding as part of the diabetes diagnosis).

Test result requires additional diagnostic testing or medical/surgical intervention.

Test result leads to a change in study drug dosing or to discontinuation from the study.

Test result is considered by the investigator to be an adverse event (i.e., any new unfavorable sign/symptom, or previous condition that has increased in severity or frequency during the study).

Laboratory abnormalities that are associated with a chronic, stable medical condition (e.g., slightly elevated ALT in a subject with hepatitis C that is unchanged or decreased from baseline) do not have to be considered clinically significant, but this judgment is left to the investigator.

Note that repeating a test to confirm an abnormal result, in the absence of any of the above, does not mean that a lab must be clinically significant. An abnormal result that is found to be in error is not clinically significant and should not be reported as an adverse event.

